## Abstract

Background: Healthcare professionals have negative implicit biases toward minority and poor patients. Few communication skills interventions target implicit bias as a factor contributing to disparities in health outcomes. We report the protocol from the COmmuNity-engaged SimULATION Training for Blood Pressure Control (CONSULT-BP), a trial evaluating a novel educational and training intervention targeting graduate medical and nursing trainees that is designed to mitigate the effects of implicit bias in clinical encounters. The CONSULT-BP intervention combines knowledge acquisition, bias awareness, and practice of bias mitigating skills in simulation-based communication encounters with racially/ethnically diverse standardized patients. The trial evaluates the effect of this 3-part program on patient BP outcomes, self-reported patient medication adherence, patient-reported quality of provider communication, and trainee bias awareness.

Methods: We designed a cluster randomized trial of the intervention among cohorts of internal medicine (IM), family medicine (FM), and nurse practitioner (NP) trainees at a single academic medical center. Within each academic year, we aimed to randomize training times to 1 of 5 start dates using a stepped wedge design. The stepped wedge design compares outcomes within training clusters before and after the intervention, as well as across exposed and unexposed clusters. However, this design was not feasible beyond the first year of our study because our study was paused during the COVID emergency. To maintain clinical staff services in the hospital, we were not able to maintain the randomization of training role out to all clinics and cohort. We aimed to enroll entire specialty cohorts of IM, FM, and NP trainees over a 3-year period, with each academic year constituting an intervention cycle, with 3 cycles of implementation corresponding to 3 sequential academic years. Due to COVID, we extended enrollment to a 4-year period. Therefore, we analyze these data as cohort study.

Primary outcome of blood pressure control is measured at the patient-level for patients clustered within trainees. Eligible patients for outcomes analysis are: English-speaking; non-White racial/ethnic minority; Medicaid recipient (regardless of race/ethnicity); hypertension; not have pregnancy, dementia, schizophrenia, bipolar illness, or other serious comorbidities that would interfere with hypertension self-control; not enrolled in hospice. Secondary outcomes include trainee bias awareness. A unique feature of this trial is the engagement of academic and

community stakeholders to design, pilot test and implement a training program addressing healthcare.

**Discussion:** Equipping clinicians with skills to mitigate implicit bias in clinical encounters is crucial to addressing persistent disparities in healthcare outcomes. Our novel, integrated approach may improve patient outcomes.

**Key words:** implicit bias; medical education; bias awareness; community engagement; simulation training

## INTRODUCTION

### Rationale for the Trial

Evidence suggests that healthcare professionals have negative explicit and implicit biases toward minority and poor patients, which can adversely affect clinical decision-making and interpersonal communication. Mitigating clinician bias through targeted training in bias awareness and interpersonal communication skills is a promising strategy for decreasing healthcare disparities for racially, ethnically, and socio-economically disadvantaged persons. Few rigorously designed trials of communication skills target implicit bias as a factor contributing to disparities in health outcomes.

To address this gap, we designed a theoretically-grounded, multi-component, training intervention trial called “COmmuNity-engaged SimULation Training for Blood Pressure Control” (CONSULT-BP). The primary aim of the trial is to improve patient outcomes using a training program that combines knowledge acquisition, bias awareness development, and simulation-based communication practice with racially and ethnically diverse patients in order to better prepare clinicians for patient interactions in which implicit bias may affect healthcare outcomes. The clinical focus of the intervention is hypertension management because it represents a challenging public health priority, with healthcare disparities and clinical outcomes mediated, in part, by the quality of clinician-patient communication, bias and unsatisfactory patient experiences of care.

The current educational arsenal to address racism and bias in healthcare has critical gaps, notably failing to incorporate personal bias awareness and evidence-based bias mitigating strategies into a program of practice and feedback from patients. We address these gaps in our trial by implementing a multi-component “knowledge, awareness, and practice” training model that involves community member and patient representation during the design and operationalization of the educational intervention. This protocol report provides a resource for others seeking to design a trial that evaluates and implements a training intervention to mitigate implicit bias in clinician-patient encounters.

### Objectives

The aims of the clinical trial are to evaluate the effect of this 3-part, training program on:

1. patient blood pressure outcomes, reported in the electronic medical record (EMR); 2. self-reported patient medication and diet adherence, as measured by the Hypertension Medication

Nonadherence Scale and the Blood Pressure Self-Care Scale; 3. patient-reported quality of provider communication, as measured by the Health Care Climate Questionnaire; 4. the trust sub-scale of the Primary Care Assessment Survey; and 5. trainee bias awareness, as measured by the Bias Awareness Scale.

**Version 3.0 updates:** Objectives 2-4 were not possible because the collection of patient self-reported data was precluded due to the COVID emergency.

## INTERVENTION

### Description of the CONSULT-BP Educational Intervention

#### Core Educational Elements

The three (3) core elements of the educational and training intervention include: 1. trainee knowledge acquisition about healthcare disparities, implicit bias and racism; 2. trainee awareness of personal bias; and 3. provision of skills to mitigate bias, along with an opportunity to practice those skills with authentic standardized patient actors. A Standardized Patient (SP) is a person carefully recruited and trained to take on the characteristics of a real patient thereby affording learners an opportunity to practice and be evaluated on learned skills in a simulated clinical environment.

To build knowledge, we used National Institute of Minority Health and Health Disparities-funded e-learning modules about health disparities, implicit bias, and patient-centered communication skills. We also deliver evidence-based practice knowledge about hypertension management, because the skills practice cases with SPs focus on hypertension management. To develop personal bias awareness, we use the Implicit Association Tests (IAT) with results feedback to the trainee. To develop skills, we present evidence-based strategies to mitigate bias previously tested in a randomized trial by Devine et al. Finally, trainees are provided an opportunity to practice those bias-mitigating skills using high-fidelity simulated clinical encounters with SPs. (**Figure 1**)

#### Theoretical Framework

The educational intervention and its delivery, conceived in 2017 and prior to more recent models for implicit bias education and management, were designed to reflect key features of an adaptation of Bennett's intercultural competency framework. In this theoretical model, to overcome *denial* about ones' own implicit biases, learners need to first acquire knowledge and

understanding about implicit bias. Then, to help learners develop *acceptance* of the effect of implicit bias on healthcare disparities, learners need to move toward *integration* and recognition of implicit bias within themselves and their clinical encounters. The ultimate goal is to motivate learners to acquire and apply effective communication skills in situations where implicit bias is likely to arise.

Applying the simulation-based training model of repeated practice and feedback for skills acquisition and progression to skill mastery, the CONSULT-BP training featured “mock” clinical encounters designed to “activate” trainee biases in the clinical care setting. To replicate the “authentic” experience of implicit bias in clinical care, the CONSULT-BP intervention developed face-to-face simulated clinical encounters with “acting” SPs recruited from local racial and ethnic communities as a foundational component of the program. These face-to-face interactions provided a “contact-based educational intervention.” Contact with groups for which one may hold biased attitudes may help reduce such bias.

## METHODS AND ANALYSIS

### Trial Design

This was originally designed as a cluster randomized trial of the CONSULT-BP training using a stepped wedge design to evaluate the effectiveness of one-time CONSULT-BP training on patient outcomes. The original rationale for the stepped wedge design accommodates pre-existing training schedules to mitigate the effect of temporal trends in clinical skill proficiency. Within cohorts of internal medicine residents, family medicine residents, and nurse practitioner students, groups of trainees were intended to be randomly assigned to 1 of 5 training time start dates in a given academic year using a stepped wedge design to accommodate pre-existing training schedules and mitigate the effect of temporal trends in clinical skill proficiency. It also allows for all trainees to be assigned to the intervention, which was a pre-condition of involvement by the participating training programs, in order to meet training requirements. This design is statistically advantageous because all trainees have control and intervention periods, everyone serves as their own control, allowing for within and across participant comparisons based on data collection both before and after the intervention. Our model randomizes training times to one of five start dates within each academic year to accommodate pre-existing training schedules and to mitigate the effect of temporal trends in clinical skill proficiency.

**Version 3.0 updates:** The cluster randomized trial design was not feasible beyond the first year of our study because our study was paused during the COVID emergency. To maintain clinical staff services in the hospital, we were not able to maintain the randomization of training within year because the needs of the training program's provision of clinical services took precedent over the didactic training. Therefore, we analyze these data as cohort study.

### **Setting**

This trial is being conducted at a single academic safety net hospital system that includes clinical delivery sites at the academic medical center, a community hospital, and three outpatient centers. Approximately 40% of medical center's primary care patients are low income and ~27% non-white. The surrounding community includes 34% of residents that do not speak English at home, 21% are Hispanic/Latinx, and there are large newcomer immigrant and refugee populations. The medical center is a major regional training site for medical students, graduate nursing students, and postgraduate medical residents. The participating training programs include the internal medicine (IM), family medicine (FM) residency training programs, and the Doctor of Nursing Practice (DNP) nurse practitioner graduate school program. Participant recruitment started in September 2018 and we will enroll trainees and patients until August 2021. Data collection will continue until November 2021.

**Version 3.0 updates:** Participant recruitment started in September 2018 and continued until we will enroll trainees and patients until August 2022. Data collection continued until December 2022.

## **PARTICIPANTS**

### **Eligibility Criteria**

#### **Trainee Enrollment**

Training programs assign their own trainees to participate in the intervention. Eligibility criteria for inclusion of trainee measures in the trial's outcomes analysis are: 1. practice at a clinical site supported by the medical center's EMR to allow data collection for BP outcome measurement; 2. a 15-week clinical look-back period; and 3. no prior completion of the CONSULT-BP intervention. Trainees are provided a fact sheet and asked to opt-out of the study if they do not want their data used for outcomes analysis.

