### **Intervention Assignment and Recruitment**

The educational intervention was integrated into the residency programs in IM and FM, and into the curriculum for DNP students. We initially aimed to enroll entire specialty cohorts of IM, FM, and NP trainees over a 3-year period, with each academic year constituting an intervention cycle, with 3 cycles of implementation corresponding to 3 sequential academic years. Due to the COVID emergency, this was extended to 4 years of enrollment across 4 academic years. Within the first pre-COVID academic year, we randomized training times to 1 of 5 start dates using a stepped wedge design. Our biostatistician used a random sequence generator to assign 5 groups of learners, from within each program, to 1 of 5 staggered intervention training dates within an academic year.

**Version 3.0 updates:** Due to COVID, randomization to training times within each academic year was not possible. Each training program schedulers assigned the trainees according to availability within the learning schedules in order to maintain clinician availability to provide care during the COVID crisis. However, across all years, the program was delivered over two in-person sessions (and via virtual teleconferencing during COVID), scheduled five weeks apart, to leverage a spaced learning design.

The sessions were designed to minimize the time burden of the intervention on trainees outside of the classroom. As such, the in-person training sessions combined multiple educational components that trainees completed individually, but as part of an onsite group session. In each educational session, components included: “individual” online didactic modules, online IATs, face-to-face clinical practice simulation with SPs, and “group-based” facilitated debriefing sessions. Originally, training in skills to mitigate the effects of implicit bias detailed by Devine et

al. was addressed as part of the group-based IAT debriefings that preceded case simulations with SPs. Each of the two, in-person sessions lasted about four hours. If trainee participants were unable to attend one of the sessions due to scheduling conflicts, we provided alternative dates for attendance.

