## **Outcome Measures and Data Collection**

### Trainee Measures

*Trainee Demographics.* We collect trainee age, gender, race/ethnicity, training year, whether they are US or foreign-born, and fluency in another language.

*Trainee IAT, Explicit Bias Measures, Bias Awareness, and Reaction to the IAT.* Trainees are asked to complete online Race/Ethnicity IATs [Black/White, Latino/White] and Race/Ethnicity-Medical Compliance IATs [Black/White, Latino/White]. Trainees were asked about their corresponding explicit beliefs and perceptions of what "other health professionals"

believe about race/ethnicity and race/ethnicity-related medical compliance in order to assess trainees' perception of their own bias as being "better than average". To assess trainees' reaction to the IAT, three questions are included from Howell & Ratliff using a 4-point scale (Strongly disagree, Disagree, Agree, Strongly Agree) to measure the trainees' degree of defensiveness to the IAT. Trainees also complete a 7-item Bias Awareness Scale, with items assessed on a 6-point scale (strongly agree to strongly disagree) and higher scores indicating greater bias awareness. In year 1, these items were collected online during each of the in-person training sessions and included 2 IATs at each session (total 4 IATs).

**Version 3.0 update:** After the first year of the intervention and in response to feedback from learners and faculty and in light of growing awareness of the need to address learner defensiveness in implicit bias education, we re-designed subsequent the CONSULT assessments to reduce the number of IATs requested, we made the IAT an optional component, and we requested completion of only one race-compliance IAT.

*Assessment of Trainees by SPs.* Community SPs complete standardized checklists of trainee performance measuring communication skills, perceptions of respect, emotional response, concern, empathy, listening skills, involvement in shared decision-making, engagement and partnership, BP measurement technique, and global performance. Standardized patient evaluators included simulation center standardized patient staff who participated in hypertension management clinical simulations with the trainees. Standardized patient evaluators were not limited in the number of trainees they could evaluate and provided ratings between September 2018-April 2022.

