#### Patient Measures

The primary trial outcome is the change in BP as reported in the EMR. Clinical measurements are collected in the 15-week control period prior to CONSULT-BP training period and during a 20-week post intervention period. The *main outcome* measures in the primary analysis will be systolic and diastolic BP (mm Hg) from the EMR. Analyses will stratify BP control as defined by the Joint National Commission 8: controlled HTN defined as SBP of <140/90 for most patients, or SBP < 150/90 for patients  $\geq 60$  years without a diagnosis of diabetes or chronic kidney disease, and uncontrolled hypertension as defined as greater than these values.

**Version 3.0 updates:** The original study design also included secondary patient self-reported outcomes including adherence to visits, diet modification and antihypertensive medication use as measured by the BP Self-Care Scale, Hypertension Medication Nonadherence Scale, and quality of communication and trust measured in the Health Care Climate Questionnaire and the trust sub-scale of the Primary Care Assessment Survey. In year 1, these surveys were administered in clinic offices of participating trainees in the 15-weeks before and 20-week after the educational intervention. This was not possible after the first year of the trial due to the COVID emergency.

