## **Statistical analysis**

**Version 3.0 updates:** To maintain clinical staff services in the hospital, we were not able to maintain the cluster randomized stepped wedge design of training role out to all clinics and cohort during the COVID emergency. Therefore, we analyze these data as cohort study.

The first step of statistical analysis was examining the distribution of all data points to identify outliers or errors in the data of primary interest. Unadjusted analysis of categorical data was conducted with chi-square tests; analysis of continuous data used analysis of variance. Mixed effects regression models were fit to estimate the relative changes of clinical outcomes (BP values and clinical cut points) for patients seen by residents in the 6 months before and 6 months following the intervention periods. Mixed-effect linear regression models (logit models for normal and optimal BP categories) were fit with mixed effects for resident ID and for study cohort. All mixed-effect models also contained terms for the additional terms to account for study composition and potential confounders: study population (race and insurance strata),

clinical department (Family Medicine vs Medicine), age and sex, and relevant clinical comorbidity(diabetes, obesity, hyperlipidemia, coronary artery disease, cerebrovascular disease, and tobacco use). In order to determine if the study intervention was differentially effective for the different patient groups (ie. white patients with Medicaid and patients of color with either private insurance, Medicare, or Medicaid), we modeled interaction terms between 4-level population variable and intervention period. P-values less than 0.05 were considered statistically significant.

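### Trainee inclusion depends on the training date and no post-training clinic time is required, so the mix of training stages can differ between the control and post periods

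*Combined protocol and SAP*

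**What the plan says.** - **Eligibility.** Trainee Enrollment lists three conditions for a trainee's data to enter the outcome analysis: practice at a site on the centre's medical record system, "a 15-week clinical look-back period", and "no prior completion of the CONSULT-BP intervention". None concerns time in clinic after training.
- **Windows.** Patient Measures states: "Clinical measurements are collected in the 15-week control period prior to CONSULT-BP training period and during a 20-week post intervention period". The Statistical analysis section instead models outcomes "for patients seen by residents in the 6 months before and 6 months following the intervention periods".
- **Schedule.** Under Intervention Assignment and Recruitment, first-year learners were randomised "to 1 of 5 staggered intervention training dates within an academic year", with two sessions "scheduled five weeks apart, to leverage a spaced learning design". The spacing of the five dates is not given. After the first year, programme schedulers chose the dates.
- **Dates of training activity.** Trainee Measures says that the standardized patients "provided ratings between September 2018-April 2022". These ratings come from the training simulations.
- **Design claim.** Trial Design says that "all trainees have control and intervention periods, everyone serves as their own control".
- **Model.** The Statistical analysis section fits effects for resident and study cohort and adjusts for patient characteristics and department. Training year is collected (Trainee Measures) but is not among the listed covariates.

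**The concern.** The look-back rule ties inclusion to the training date. A trainee who has just joined and is trained early has too little prior clinic time and is excluded. Because prior completion is also an exclusion, that trainee cannot come back in later. The same person given a later date is included. In the randomised year, inclusion can therefore depend on the randomised assignment.

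Nothing mirrors this at the other end. A trainee who is trained late and then leaves contributes a full control window and a shortened post window.

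Together, these can make the trainees behind the control readings differ in training stage from those behind the post readings. The estimated change in blood pressure could then partly reflect differences between junior and senior trainees. Drift in trainee skill over time is one of the threats that Trial Design says the staggered start was meant to limit. After the first year, randomisation no longer balances the dates.

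**Working it through.** **1. The plan's own figures.** The Sample size calculation uses 3 blocks before and 4 after, of 5 weeks each: 3 × 5 = 15 weeks and 4 × 5 = 20 weeks, in line with Patient Measures. Its counts reproduce: 205 × 10 = 2,050 control and 205 × 20 = 4,100 post observations. These counts give every trainee both windows in full, with no allowance for exclusion or truncation. The plan states no figure for how the windows fit the calendar, so there is none to reproduce.

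**2. Look-back for a new trainee.** Assume entry on 1 July 2018.
- To 1 September: 62 days / 7 = 8.9 weeks.
- To 30 September: 91 days / 7 = 13.0 weeks.
- 15 weeks = 105 days, reached on 14 October 2018.

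A new trainee trained at any time in September falls short. From 14 October the same trainee qualifies.

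**3. Follow-up for a leaver.** Assume departure on 30 June 2022 and a last session in April 2022.
- From 1 April: 90 / 7 = 12.9 weeks, or 64% of 20.
- From 30 April: 61 / 7 = 8.7 weeks, or 44% of 20.

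**4. Fit within one year.** This matters only for trainees present for a single year, taken as 52 weeks.
- One start date needs 15 + 5 + 20 = 40 weeks, leaving 12.
- Five dates have four gaps, so they fit if spaced 12 / 4 = 3 weeks apart or less.
- At one block (5 weeks, assumed) they need 40 + 4 × 5 = 60 weeks, 8 too many.
- With a first date in September (weeks 8.9 to 13.0) and 5-week spacing, the fifth date starts at weeks 28.9 to 33.0 and training ends at weeks 33.9 to 38.0. That leaves 52 − 33.9 = 18.1 down to 52 − 38.0 = 14.0 weeks, a loss of about 2 to 6 of 20. One or two of the five dates fall before week 15.
- With the 6-month windows, one start date needs about 26 + 5 + 26 = 57 weeks, so no single-year trainee can have both windows in full. The 15-week criterion does not secure a 6-month look-back either.

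**5. Possible size.** The shares of entrants and leavers are not given. Assume equal numbers on each date and the September, 5-week schedule of step 4. Trainees truncated at the fifth date are then (leaver share) × 1/5: 0% if there are no leavers, 1/3 × 1/5 = 6.7% if one third are, and 20% if all are. New trainees excluded are (entrant share) × 1/5 to 2/5. For a one-third share this is 6.7% to 13.3%.

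**6. Power.** No standard deviation is stated. Assuming 20 mmHg, a two-sided 5% test and no clustering, power for 3 mmHg in uncontrolled hypertension (1,025 control, 2,050 post) is 97.5%. Suppose one third of trainees are new and two of five dates exclude them. The retained fraction is 1 − 0.4/3 = 0.867, and power is about 95%. On these assumptions selection is the main issue, and the loss of power is small.

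**7. What the model absorbs.** If the resident term is a random intercept, the period estimate is a weighted average of the within-trainee change and the between-trainee comparison. The between-trainee part carries more weight when correlation within trainees is low. Unequal training-stage mix can enter through that part, and no listed covariate adjusts for it.

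**The case against.** A reader might infer that five start dates cannot fit in an academic year. The documents do not support that. They give no spacing, and with the 15- and 20-week windows, dates 3 weeks apart or less fit. Only the training dates must fall within the year. Continuing trainees' windows can cross into the next one, and data collection ran to December 2022.

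A reader might also combine a 40% loss of follow-up at the last date (8 of 20 weeks) with exclusions at the first. These need incompatible schedules. The 8-week loss requires a first date at week 15, when no new trainee fails the look-back. A September first date at one-block spacing leaves about 14 to 18 of the 20 weeks.

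Nor is the own-control statement in Trial Design shown to be false. A shortened post period is still a post period, and the sentence belongs to the rationale for the stepped wedge, which the Version 3.0 update replaces with a cohort analysis.

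The resident effects already make much of the contrast within trainee, and unequal control and post counts were planned. The September and April ratings could come from make-up sessions, since alternative dates were offered. All of this stands and limits the size of the point. It does not supply a follow-up criterion, put training stage in the model, or show that random effects remove all of the between-trainee mix.

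**Conclusion.** The point holds in a limited form. Inclusion depends on the training date, no post-training clinic time is required, and training year is left out of the models although it is collected. On an assumed 1 July start, new trainees trained in September 2018 are excluded with at most 13.0 weeks of look-back, while those dated from mid-October are kept. On an assumed 30 June departure, leavers who finish in April 2022 have 8.7 to 12.9 of 20 post weeks. The training-stage mix can therefore differ between periods.

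How far it does so is unknown without the start dates, their spacing, and the shares of entrants and leavers. The direction and size of any bias in mmHg cannot be derived from the documents. The reason to act is that the remedy uses data already held and costs little.

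**What to change.** 1. Add training year to the models in the Statistical analysis section.
2. Estimate the period effect within trainee, as the primary or a key sensitivity analysis. Either use resident fixed effects, or keep the random intercept and enter separate within- and between-resident period terms. The second form also suits the logit models. Trainees with readings in only one period then do not inform the within-trainee estimate.
3. Beside the all-trainee analysis, report a sensitivity analysis in trainees with both windows in full. Requiring only some readings in each window would keep the truncated leavers. Requiring full windows conditions on remaining in clinic, so this should not replace the all-trainee result.
4. Qualify the own-control statement in Trial Design with a table of trainees who have full, truncated or no control and post periods, by start date and training year. Include those excluded for insufficient look-back, and show the randomised year separately. Use one window definition throughout, since the 15/20-week and 6-month definitions must be reconciled before anyone can be counted as complete.

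The cost is slightly wider intervals and a little more analysis work. No new data are needed. A within-trainee estimate does not remove a trainee's own improvement over time or calendar trends, and it cannot restore trainees excluded by the look-back rule. The table is needed for that reason.
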